16.4 REPORTING AND COMMUNICATION OF RESULTS

All information and data generated in association with this study will be held in strict confidence and remains the sole property of PI.

16.5 CLINICAL TRIAL TERMINATION

A subject's participation in the clinical trial will be terminated if the Investigator believes it is in the subject's best medical interest or if the subject no longer complies with the clinical trial requirements. The subject may also decide to withdraw from the clinical trial at any time and terminate participation. The IRB and/or other Regulatory Authorities may decide to interrupt this clinical trial if either believes that this is necessary.

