Treatment subjects will be assessed for any adverse device effects (ADE), T6/T7 dermatome assessment, review and download of diary data, and stimulation adjustment (if needed). If skin irritation is present, PI will classify as Mild, Moderate or Severe and confirm system compliance (wipes, lotion, patch rotation, etc.). Mild irritation may require up to 3 days without stimulation. Moderate irritation may require up to 2 weeks without stimulation. Severe irritation may require medical attention and study termination. PI or designee will assess when irritation is present and review for resolution. Treatment subjects will be discharged with the smartphone application and the Elira wearable patch system and instructions on use. Treatment subjects will be instructed to return with the Elira wearable patch system and smartphone app at their next scheduled visit. Treatment subjects may be contacted by PI or clinical coordinator periodically through the trial to address any questions or concerns related to device function.

End of Study Visit 8 (week 24; ± 7 days) – Treatment & Control subjects will be assessed for adverse events, changes to concomitant medications and commitment to exclusion criteria. Physical including weight, requisition for laboratory tests, blood

Protocol #: CD-005; Version #: 4.0

Original Date: May 8, 2018 Revision Date: May 3, 2019

-Confidential-

	
pressure, labs, and urine pregnancy test for FOCBP, and completion of questionnaires (– PHQ9, TFEQ-R18V2, and Patient Preference Survey). Collect, and review paper diaries. This visit may be rescheduled if the paper diaries were not completed the week prior.
 
Treatment Group Only- Complete End of Study Questionnaires- subjects will return the Elira wearable patch system and the smartphone application. Treatment subjects will be assessed for ADEs and have their T6/T7 dermatome area examined. Treatment subjects will be photographed (below the neck) in similar attire to their initial visit for weight loss reference.

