5. STUDY DESIGN

[figure not shown]
Randomized, adaptive parallel arm study. Subjects will be initially screened during a screening period (1 week, ± 7 days; Figure 2). During this screening period, prior to study procedures being performed, subjects will sign an informed consent form. Then they will have their weight and blood pressure measured, FOCBP will have a pregnancy test, get blood drawn for analysis (blood lipids, HbA1c), and complete patient preference questionnaires. At the end of the screening/baseline period, eligible subjects will be offered the chance to enroll in the study. After enrolling, subjects will be randomized to treatment or control groups.

The Treatment group will be instructed to follow a healthy diet that they will follow for the duration of the study and will receive training on the use of the paper diaries, electronic scale, smartphone app and the Elira wearable patch system. All treatment subjects will be required to stimulate in the office for up to 30minutes to confirm sufficient system training and to acknowledge understanding stimulation settings. A below neck photograph will be taken of the treatment group in requested attire (i.e. biker shorts and sports bra for women, biker shorts for men). Following this, subjects will enter the Therapy Period, for a ~24-week duration. Treatment subjects may be contacted by PI or clinical coordinator to address any questions related to device functionality or compliance. Device usage will be monitored throughout therapy phase to ensure proper functionality and subject safety.

The Control group will be instructed to follow a healthy diet that they will follow for the duration of the study and will receive training on the use of the weekly paper diary and electronic scale. The Control group will not receive the electronic smartphone app or the Elira wearable patch system/components.

At the end of the 3 months of the Therapy Period, all subjects will be assessed for weight loss, blood pressure, blood lipids, HbA1c, and will continue to participate through months 4-6 to confirm the long term safety of the device prior to being terminated from the study. A below neck photograph will also be taken at the 12 week visit.

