7.3 SELECTION AND ENROLLMENT OF SUBJECTS

Prospective study subjects will be screened for study eligibility. A subject is considered enrolled after:

1. Written Informed Consent is obtained.
2. Meeting all inclusion and exclusion criteria and randomized into the study.
3. This study will utilize unique subject numbers for the purpose of trial data collection. Subjects signing an Informed Consent but not meeting all criteria will not be considered enrolled in the study, but the signed Informed Consents will be maintained by the PI for seven (7) years.

Following enrollment, subjects should remain in the study until completion of the required Therapy Phase.

A subject's participation may be discontinued for the following reasons:

- Subject Withdrawal: As subject participation in a clinical trial is voluntary, the subject may choose to discontinue participation at any time without penalty or loss of benefits.

- Investigator Termination: The Investigator may terminate the subject's participation without regard to the subject's consent if the Investigator believes termination is medically necessary.
- Lost-to-Follow-up: A subject is lost-to-follow up if he/she does not complete required follow-up, but has not "officially" withdrawn consent. In order to consider a subject lost to follow-up, site personnel should make all reasonable efforts to locate and communicate with the subject. A minimum of three (3) attempts to contact the subject should be recorded in the source documentation including date, time and name of site personnel attempting to make contact.

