8.1.2 Analysis Populations

The intent to treat (ITT) analysis population is defined as all subjects who were enrolled.

The modified intent to treat (mITT) analysis population is defined as all subjects who initiated therapy (i.e., initiated their first Treatment Period Visit) and had data through week 12. All safety and effectiveness analyses will be completed on the mITT analysis population.

The per protocol (PP) analysis population is defined as all subjects who met all inclusion/exclusion criteria, completed all visits in the study without any major protocol deviations. All effectiveness analyses will be completed on the PP analysis population.

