8.3 Handling of Missing Data

Every effort will be made to collect all data at each time point in the study. The PI and the Clinical Data Monitor will minimize the amount of missing data by appropriate management of the prospective clinical trial, proper screening of subjects, and training of clinicians. If a subject misses a dietary entry in to either the paper or electronic diary, a look back entry for that value is allowed provide for the week preceding the event. Outside this window, data will be considered missing. All partial data available for subjects who drop out during the course of the study will be included.

Missing data will only be imputed for the co-primary endpoints. The LOCF method will be utilized at the 3 month time point for the two co-primary endpoints of percent change from baseline in appetite suppression scores and %TBWL. The ANCOVA analysis with LOCF on the mITT population for the co-primary endpoints were planned for the main analyses for the study to determine study success. Note, however, by definition, the mITT population may not need LOCF as only those with a week 12 visit will be included in the mITT population. A patient, however, may have had a week 12 visit but have missing data on some or all co-primary endpoints, in which case LOCF methods will be used.

To assess the potential effect of missing data on the co-primary effectiveness endpoints, a tipping point analysis will be computed for each co-primary endpoint on the mITT population. If none of the 5 co-primary endpoints are missing at week 12, the tipping point analysis will be a moot point and will not be conducted. A tipping point analysis involves imputing each missing data point, one-at-a-time until the study conclusion is tipped in the other direction (i.e., from statistically significant to non-statistically significant or vice versa, from non-statistically significant to statistically significant).8.4 Subject Population for Safety and Effectiveness Analysis

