9.8 QUESTIONNAIRES

All subjects will be required to complete the Pre-Study Survey and PHQ-9 at screening/baseline visit. All subjects will be required to complete a VAS diary for hunger and fullness according the following schedule: 1 day with 8 entries following enrollment (approximately week 0-1), 1 day with 8 entries following the 4, 8, 12, 16 and 20-week visit (approximately week 4) and 1 day with 8 entries in the last week of the study (approximately week 24). All subjects will be required to complete the TFEQ-R18V2 at enrollment and at each Therapy Visit (Appendix 3). All subjects will be required to complete PHQ9-, TFEQ-R18V2 and End of Study Questionnaire at the last study visit (Visit 8 or early termination visit).

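### Section 16.5 ends participation for non-compliance, and the available text requires no week-12 weight or diary from subjects terminated before week 12

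*Combined protocol and SAP*

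**What the plan says.** Section 16.5 requires that participation be ended if the investigator thinks this is in the subject's medical interest, "or if the subject no longer complies with the clinical trial requirements". It gives no threshold and no warning step.

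Section 7.3 lists three reasons for discontinuation: withdrawal by the subject, termination by the investigator, and loss to follow-up. Investigator termination there is discretionary, applies "if the Investigator believes termination is medically necessary", and may be done without the subject's consent. The default in 7.3 is that enrolled subjects stay to the end of the Therapy Phase.

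The Visit Schedule in the Protocol Summary adds a device-related route: "Severe irritation may require medical attention and study termination".

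Section 5 says that at 3 months "all subjects will be assessed for weight loss". The only mention of an early termination visit is in 9.8, where questionnaires are due "at the last study visit (Visit 8 or early termination visit").

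On analysis, 8.1.2 defines mITT as subjects who "initiated their first Treatment Period Visit) and had data through week 12", and 8.3 confirms that "only those with a week 12 visit will be included in the mITT population". Section 8.3 also says: "All partial data available for subjects who drop out during the course of the study will be included". Section 8.4 defines the same set by start of therapy alone, with no week-12 condition.

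**The concern.** Weight at week 12 can be measured in anyone who attends, whether or not they used the device. A rule that ends participation for non-compliance gives up that measurement, and no later choice of analysis set can recover it. Both the %TBWL and the appetite co-primary endpoints are affected.

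The loss need not be equal between arms. Device duties, device-use monitoring and electrode irritation exist only in Treatment. Controls have duties they can breach too: no other weight-loss programme or new fitness regimen (7.2.19), and stable medication (9.7). Eligibility is re-checked at every visit in both arms, so there is regular occasion to apply the clause. Treatment is open-label, so whoever applies it knows the arm.

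If terminated subjects would have lost less weight than the others, and more of them come from one arm, the comparison of those who remain is biased. LOCF and the tipping-point analysis are both run on mITT. Under 8.1.2 and 8.3 neither reaches a subject terminated before week 12.

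**Working it through.** **1. Who is affected, from the text.**
- Subjects who pause or stop stimulation but stay enrolled are not at issue. Section 5, the Visit Schedule and Appendix 6 keep them on scheduled visits with a week-12 weight.
- Subjects terminated between weeks 12 and 24 may already have week-12 data and can remain in mITT.
- Subjects terminated before week 12 have no required week-12 weight or diary. Under 8.1.2 and 8.3 they are outside mITT. Under 8.4 they stay in with an earlier weight carried forward.

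**2. The plan's own figure.** The point disputes no number in the plan, but it uses 80 per group from 8.2. With means of 3.5% and 6%, SD 5, 80% power and two-sided 0.05 (assumed from the 95% two-sided intervals in 8.1.1), n = 2(1.96 + 0.842)² × 5² / 2.5² = 62.8, so 63 per group. Then 63 × 1.30 = 82, close to the stated 80. (63 / 0.70 = 90 would be the usual inflation for 30% dropout; that is a separate matter.)

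**3. Illustration for %TBWL, complete cases.** From 8.2: mean loss 3.5%, SD 5, 80 per arm. Assumed, because the documents give nothing: no true effect, all terminations before week 12, shares pT and pC terminated, and a mean loss m of 0% to 2% that terminated subjects would have had at week 12.

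- Retained mean in an arm = (3.5 − p·m) / (1 − p)
- Bias = retained Treatment mean − retained Control mean
- SE = 5 × √[1/(80(1 − pT)) + 1/(80(1 − pC))]
- Type I error = P(Z > 1.96 − bias/SE) + P(Z < −1.96 − bias/SE)

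Worked case, 20% versus 10%, m = 0: 3.5/0.80 = 4.375 and 3.5/0.90 = 3.889, so bias = 0.486; SE = 5 × √(1/64 + 1/72) = 0.859; type I error = 8.7%.

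| Loss, Treatment vs Control | m | Bias (points) | SE | Type I error |
|---|---|---|---|---|
| equal (e.g. 10% vs 10%) | 0 or 2 | 0 | 0.833 | 5.0% |
| 10% vs 5% | 2 | 0.088 | 0.822 | 5.1% |
| 10% vs 5% | 0 | 0.205 | 0.822 | 5.7% |
| 15% vs 5% | 2 | 0.186 | 0.835 | 5.6% |
| 15% vs 5% | 0 | 0.433 | 0.835 | 8.1% |
| 20% vs 10% | 2 | 0.208 | 0.859 | 5.7% |
| 20% vs 10% | 0 | 0.486 | 0.859 | 8.7% |

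Reversing the arms reverses the sign. If terminated subjects would have lost the same 3.5%, the bias is 0 for any split.

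**4. Terminations counted inside the plan's 30% dropout.** With 80 × 0.70 = 56 retained per arm and the rest of the dropout random, SE = 5 × √(2/56) = 0.945. The 15% versus 5% and 20% versus 10% splits then give 5.4% to 8.1%.

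**5. Under the 8.4 wording with LOCF.** Bias = pT·eT − pC·eC, where e is the carried weight loss minus the true week-12 value, and SE = 5 × √(2/80) = 0.791. For 20% versus 10% and errors of up to 2 points:
- same error in both arms: 0.40 − 0.20 = 0.20 points, 5.7%
- error in Treatment only: 0.40 points, 8.0%
- opposite errors: 0.40 + 0.20 = 0.60 points, 11.8%

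LOCF therefore offers no small guaranteed bound.

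**The case against.** **Section 16.5 may add to 7.3 rather than contradict it.** The clause in 7.3 covers termination regardless of consent, so 16.5 can be read as one more ground. Part of the document directly after the 7.3 list was not available to us. A reader might infer a proven conflict between the two sections. The available text supports only that non-compliance is absent from the reasons we can see.

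**The early termination visit may collect more than questionnaires.** Section 9.8 treats it as an alternative to Visit 8, and the Visit 8 column in Appendix 6 includes weight, paper-diary collection and adverse-event review. That column carries a footnote 7 whose text is missing from our copy. It would therefore be unsafe to say that the schedule makes no provision for this visit. Even on the generous reading, the weight is taken at termination and not at week 12.

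**Non-compliance might seem already handled by the per-protocol set and by deviation reporting.** This is weak support either way. Section 13.3 defines deviations by investigator or site conduct, so a subject's failure to use the device is not clearly one.

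**The numbers are assumed, and retention is already the aim.** Both are true. The documents give no termination rates, arm split or outcomes for these subjects. Sections 7.3 and 8.3 already state retention and complete data collection as goals. Some non-compliers will simply have stopped attending, and no rule recovers their weight.

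What remains is that 16.5 states a mandatory rule whose effect before week 12 is to stop collection of co-primary data from people who may still be willing to attend.

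**Conclusion.** The concern holds for subjects terminated before week 12. It is an avoidable and possibly unequal loss of co-primary data, and its size and direction are not documented. The illustrated effects on %TBWL run from none to about half a point and 8.7% in the complete-case setting. They depend wholly on the assumed rates, split and outcomes.

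Three stronger readings are not supported:
- That every terminated subject drops out of the main analysis. This fails for terminations after a completed week-12 assessment, and under 8.4. The clash between the two mITT definitions is a separate defect.
- That the clause favours the device. Controls can also be terminated, and the bias can be zero or run the other way.
- That 8.7% is the trial's false-positive rate. The figures concern %TBWL alone. The plan declares success if any of five variables is significant, so 5% is not the study-level baseline. No figure was worked out for the diary scores.

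This is worth fixing because it is cheap, not because a large bias has been shown.

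**What to change.** - Delete the non-compliance clause from 16.5 and align the section with 7.3.
- State in 16.5, in 7.3 and in the irritation text of the Visit Schedule that stopping the device, for irritation or any other reason, ends stimulation and not follow-up.
- Record a subject's non-compliance as a deviation, and widen 13.3 to cover subject conduct.
- Keep these subjects, in both arms, on the existing visits unless they withdraw consent for follow-up. Collect at least week-12 weight and diary, and review adverse events and adverse device effects through week 24.

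The cost is a protocol amendment and possibly a consent-form change, with IRB approval before use (13.1). Sites must stay in contact with subjects who are off the device, but no new visit type is needed. Data from those who stop attending will still be missing, and the estimated effect may be slightly less favourable.

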16.6 PROTOCOL MODIFICATIONS AND DEVIATIONS

The PI will submit Protocol modifications to the IRB as necessary.

18. APPENDICES

18.1 APPENDIX 1: BMI RANGES TARGETED FOR MEN AND WOMEN ENROLLED IN STUDY (AN EXAMPLE OR NIH ONLINE SOURCE)^{15,16}

Males (target BMI indicated by Black Bars):

WEIGHT lbs	100	105	110	115	120	125	130	135	140	145	150	155	160	165	170	175	180	185	190	195	200	205	210	215
kgs	45.5	47.7	50.0	52.3	54.5	56.8	59.1	61.4	63.6	65.9	68.2	70.5	72.7	75.0	77.3	79.5	81.8	84.1	86.4	88.6	90.9	93.2	95.5	97.7
HEIGHT in/cm	Underweight				Healthy				Overweight				Obese				Extremely obese							
5'0" - 152.4	19	20	21	22	23	24	25	26	27	28	29	30	31	32	33	34	35	36	37	38	39	40	41	42
5'1" - 154.9	18	19	20	21	22	23	24	25	26	27	28	29	30	31	32	33	34	35	36	36	37	38	39	40
5'2" - 157.4	18	19	20	21	22	22	23	24	25	26	27	28	29	30	31	32	33	33	34	35	36	37	38	39
5'3" - 160.0	17	18	19	20	21	22	23	24	24	25	26	27	28	29	30	31	32	32	33	34	35	36	37	38
5'4" - 162.5	17	18	18	19	20	21	22	23	24	24	25	26	27	28	29	30	31	31	32	33	34	35	36	37
5'5" - 165.1	16	17	18	19	20	20	21	22	23	24	25	25	26	27	28	29	30	30	31	32	33	34	35	35
5'6" - 167.6	16	17	17	18	19	20	21	21	22	23	24	25	25	26	27	28	29	29	30	31	32	33	34	34
5'7" - 170.1	15	16	17	18	18	19	20	21	22	22	23	24	25	25	26	27	28	29	29	30	31	32	33	33
5'8" - 172.7	15	16	16	17	18	19	19	20	21	22	22	23	24	25	25	26	27	28	28	29	30	31	32	32
5'9" - 175.2	14	15	16	17	17	18	19	20	20	21	22	22	23	24	25	25	26	27	28	28	29	30	31	31
5'10" - 177.8	14	15	15	16	17	18	18	19	20	20	21	22	23	23	24	25	25	26	27	28	28	29	30	30
5'11" - 180.3	14	14	15	16	16	17	18	18	19	20	21	21	22	23	23	24	25	25	26	27	28	28	29	30
6'0" - 182.8	13	14	14	15	16	17	17	18	19	19	20	21	21	22	23	23	24	25	25	26	27	27	28	29
6'1" - 185.4	13	13	14	15	15	16	17	17	18	19	19	20	21	21	22	23	23	24	25	25	26	27	27	28
6'2" - 187.9	12	13	14	14	15	16	16	17	18	18	19	19	20	21	21	22	23	23	24	25	25	26	27	27
6'3" - 190.5	12	13	13	14	15	15	16	16	17	18	18	19	20	20	21	21	22	23	23	24	25	25	26	26
6'4" - 193.0	12	12	13	14	14	15	15	16	17	17	18	18	19	20	20	21	22	22	23	23	24	25	25	26

Females (target BMI indicated by Black Bars):

WEIGHT lbs	100	105	110	115	120	125	130	135	140	145	150	155	160	165	170	175	180	185	190	195	200	205	210	215
kg	45.5	47.7	50.0	52.3	54.5	56.8	59.1	61.4	63.6	65.9	68.2	70.5	72.7	75.0	77.3	79.5	81.8	84.1	86.4	88.6	90.9	93.2	95.5	97.7
HEIGHT in/cm	Underweight					Healthy					Overweight					Obese			Extremely obese					
5'0" - 152.4	19	20	21	22	23	24	25	26	27	28	29	30	31	32	33	34	35	36	37	38	39	40	41	42
5'1" - 154.9	18	19	20	21	22	23	24	25	26	27	28	29	30	31	32	33	34	35	36	36	37	38	39	40
5'2" - 157.4	18	19	20	21	22	22	23	24	25	26	27	28	29	30	31	32	33	33	34	35	36	37	38	39
5'3" - 160.0	17	18	19	20	21	22	23	24	24	25	26	27	28	29	30	31	32	32	33	34	35	36	37	38
5'4" - 162.5	17	18	18	19	20	21	22	23	24	24	25	26	27	28	29	30	31	31	32	33	34	35	36	37
5'5" - 165.1	16	17	18	19	20	20	21	22	23	24	25	25	26	27	28	29	30	30	31	32	33	34	35	35
5'6" - 167.6	16	17	17	18	19	20	21	21	22	23	24	25	25	26	27	28	29	29	30	31	32	33	34	34
5'7" - 170.1	15	16	17	18	18	19	20	21	22	22	23	24	25	25	26	27	28	29	29	30	31	32	33	33
5'8" - 172.7	15	16	16	17	18	19	19	20	21	22	22	23	24	25	25	26	27	28	28	29	30	31	32	32
5'9" - 175.2	14	15	16	17	17	18	19	20	20	21	22	22	23	24	25	25	26	27	28	28	29	30	31	31
5'10" - 177.8	14	15	15	16	17	18	18	19	20	20	21	22	23	23	24	25	25	26	27	28	28	29	30	30
5'11" - 180.3	14	14	15	16	16	17	18	18	19	20	21	21	22	23	23	24	25	25	26	27	28	28	29	30
6'0" - 182.8	13	14	14	15	16	17	17	18	19	19	20	21	21	22	23	23	24	25	25	26	27	27	28	29
6'1" - 185.4	13	13	14	15	15	16	17	17	18	19	19	20	21	21	22	23	23	24	25	25	26	27	27	28
6'2" - 187.9	12	13	14	14	15	16	16	17	18	18	19	19	20	21	21	22	23	23	24	25	25	26	27	27
6'3" - 190.5	12	13	13	14	15	15	16	16	17	18	18	19	20	20	21	21	22	23	23	24	25	25	26	26
6'4" - 193.0	12	12	13	14	14	15	15	16	17	17	18	18	19	20	20	21	22	22	23	23	24	25	25	26

18.2 APPENDIX 2: TENS UNIT USER MANUALS (ADDITIONAL FILE SUBMITTED SEPARATELY)

ELIRA

EDP ON-BODY DEVICE

[figure not shown]

PATIENT INSTRUCTIONS FOR USE

CAUTION - Investigational device. Limited by Federal (or United States) law to investigational use.

A: INITIAL SETUP with CLINICIAN

- 1 Snap on Electrode Patch**
Snap the electrode patch to the EDP.

[figure not shown]

DO NOT remove the protective liner from the electrode patch.
- 2 Register Account**
Start the Elira app on the phone provided. Proceed with registration steps.

[figure not shown]

- 3 Turn on EDP**
Turn the EDP on by pressing and holding the button 10 seconds and releasing it.

- 4 Turn on EDP**
Follow the on-boarding process required by the app.
- 5 Remove Liner**
Remove the electrode patch protective liner.

- 6 Place EDP**
Place the EDP at T6 dermatome location.

SYSTEM COMPONENTS

ELIRA

Elira Therapeutics
anNdsakfal
kNADkoasdf, ha 23443

C: DAILY USE

[figure not shown]
- 1 Snap on the Patch**
Upon waking remove EDP from charging pad.

DO NOT remove the protective liner from the electrode patch.
- 2 Turn on EDP**
Turn the EDP on by pressing and holding the button 10 seconds and releasing it.

- 3 Remove Liner**
Remove the electrode patch protective liner.

[figure not shown]

- 4 Place EDP**
Place the EDP at T6 dermatome location.

- 5 Treatment cycle**
Follow prescribed treatment cycle.

- 6 Remove EDP**
Remove EDP before bed, apply the protective liner to the electrode patch for overnight storage.

- 7 Charge EDP Overnight**
Place EDP on charger. Disconnect Bluetooth connection.

- 8 Log Dairy Post**
Complete diary entry for the day.

D: PATCH LIFE

The electrode patch life will vary, depending on care and skin type, but should be replaced when it no longer adheres well to the skin. If your skin type is oily or has residue on it, you may need to replace the electrode pad more frequently.

E: SYSTEM STATUS

THERAPY LIGHT

The Status LED blinks GREEN once ever 10 seconds while the device is in Therapy mode.

ERROR LIGHT

Low Battery - The Status LED blinks RED in high frequency.

Error Events:
Impedance out of range
Temperature out of range
Max Session Count Reached
Device Mode Error
The Status LED blinks RED in low frequency.

CAUTION - Investigational device. Limited by Federal (or United States) law to Investigational use.

ELIRA

**18.3 APPENDIX 3: PHQ-9
QUESTIONNAIRE**

PATIENT HEALTH QUESTIONNAIRE-9 (PHQ-9)

Over the last 2 weeks, how often have you been bothered by any of the following problems? (Use "✓" to indicate your answer)

	Not at all	Several days	More than half the days	Nearly every day
1. Little interest or pleasure in doing things	0	1	2	3
2. Feeling down, depressed, or hopeless	0	1	2	3
3. Trouble falling or staying asleep, or sleeping too much	0	1	2	3
4. Feeling tired or having little energy	0	1	2	3
5. Poor appetite or overeating	0	1	2	3
6. Feeling bad about yourself — or that you are a failure or have let yourself or your family down	0	1	2	3
7. Trouble concentrating on things, such as reading the newspaper or watching television	0	1	2	3
8. Moving or speaking so slowly that other people could have noticed? Or the opposite — being so fidgety or restless that you have been moving around a lot more than usual	0	1	2	3
9. Thoughts that you would be better off dead or of hurting yourself in some way	0	1	2	3

FOR OFFICE CODING 0 + _____ + _____ + _____
=Total Score: _____

If you checked off any problems, how difficult have these problems made it for you to do your work, take care of things at home, or get along with other people?

Not difficult at all

Somewhat difficult

Very difficult

Extremely difficult

Developed by Drs. Robert L. Spitzer, Janet B.W. Williams, Kurt Kroenke and colleagues, with an educational grant from Pfizer Inc. No permission required to reproduce, translate, display or distribute.

Subject Initials: _____

Date: _____

Protocol #: CD-005; Version #: 4.0

Original Date: May 8, 2018 Revision Date: May 3, 2019

-Confidential-

